Ten nurses from Mobile WACH studies will be presented with client messages from previous Mobile WACH studies, annotated with urgency predictions from the top 3 best performing NLP models. Each nurse will be asked to report their agreement with each prediction. The model with the highest sensitivity and specificity compared with the nurse “gold standard” determination will be selected for implementation in the Mobile WACH system.

Aim 2: Using a human-centered design approach, adapt the Mobile WACH system nurse interface to dynamically display urgent incoming messages.

Interactive focus groups will be conducted with 6-10 nurses from Mobile WACH studies and MOH facilities to collectively design a user interface that integrates real-time urgency classification of incoming messages and highlights messages classified as urgent.

Aim 3: Pilot the adapted Mobile WACH interface (AI-NEO) that identifies urgent client SMS and evaluate its acceptability and effect on nurse response time.

We will enroll 80 pregnant women to receive the AI-NEO SMS intervention. Women will be enrolled at 28-36 weeks gestation and will receive automated SMS regarding neonatal health from enrollment until 6 weeks postpartum, and will have the ability to interactively message with study nurses. Participant messages will be automatically categorized by urgency. We will evaluate intervention acceptability and recommended improvements among clients and nurses using quantitative and qualitative data collection at study exit (quantitative questionnaires with all client participants and qualitative interviews with 4 nurses). We will compare nurse response time to urgent and non-urgent participant messages with the ongoing Mobile WACH NEO trial, in which a non-adapted Mobile WACH system is used.

1.6 Study design. Provide a one-sentence description of the general study design and/or type of methodology.

Your answer will help HSD in assigning applications to reviewers and in managing workload. Examples: a longitudinal observational study; a double-blind, placebo-controlled randomized study; ethnographic interviews; web scraping from a convenience sample of blogs; medical record review; coordinating center for a multi-site study.

Mixed methods design phase followed by pilot longitudinal cohort study.

1.7 Intent. Check all the descriptors that apply to your activity. You must place an “X” in at least one box.

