Mobile health (mHealth) interventions can provide on-demand information and support families to improve maternal child health.

mHealth tools, which utilize mobile phones and other wireless technologies to support health, provide an attractive strategy to augment community-based care and connect households to CHV support more efficiently and frequently. More households in low-income countries own a mobile phone than have access to electricity or adequate sanitation.⁸ According to the Communications Authority of Kenya, there are now 46 million phone subscriptions in Kenya, for a national population of 43 million.⁹ **A World Bank report found that Kenyans living at the so-called economic “bottom of the pyramid” reported health information and communication was the service they most wanted to receive through their mobile phones.**¹⁰

Our collaborative team has developed an open-source human-computer hybrid SMS platform, Mobile WACH (Mobile Solutions for Women’s and Children’s Health).¹¹ Mobile WACH sends pre-composed messages to clients at scheduled times. Clients may send messages at any time; a live HCW answers incoming messages, leading to personalized dialogue. The internet-based HCW interface contains a dashboard designed to facilitate HCW management of tasks such as message response, patient tracking, and message translation into English. The system back-end collects SMS metadata such as time stamps and delivery status, as well as data on seminal events such as childbirth. To date, Mobile WACH has been implemented in 7 studies (including 4 randomized controlled trials, RCTs) targeting a range of reproductive, maternal, neonatal and child health outcomes. Scheduled intervention messages were developed for each study based on formative research with the target population,^{12–14} and behavioral theory selected based on the target outcome (Social Cognitive Theory,^{15,16} Theory of Planned Behavior,^{17,18} or Information-Motivation-Behavior Change Theory^{19,20}). All studies also allowed unstructured, personalized dialogue between clients and HCWs. **This suite of studies provides well-developed software and rich data (400,000 SMS) for the proposed project (Table 1).**

[figure not shown]
Table 1. Mobile WACH study summary

Study	Primary outcome	N clients	N SMS			Follow-up period
			Automated system	Personalized nurse	Client	
Mobile WACH XY RCT ¹⁷	Family planning	130	6,852 (144 unique)	3,356	3,577	Preg - 6mo

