Figure 3. Precision-recall curves for urgency models

The ongoing Mobile WACH NEO RCT presents an opportunity to evaluate feasibility and performance of NLP models in practice

While model performance relative to a known label can be summarized using variables such as precision and recall, the utility of NLP for improving efficiency of nurse workflow must be determined empirically. We therefore propose to conduct a pilot study in which we compare nurse workflows when using the conventional Mobile WACH platform vs. workflows when using an NLP-enabled Mobile WACH platform. An ongoing RCT, Mobile WACH NEO, is evaluating use of the Mobile WACH platform to support neonatal health in Nairobi and Western Kenya. In this proposal, we will compare workflow in the context of the Mobile WACH NEO RCT with workflow in an NLP-enabled variant of the same intervention (named AI-NEO).

1.9 Supplements. Check all boxes that apply, to identify relevant Supplements that should be completed and uploaded to **Zipline**.

This section is here instead of at the end of the form to reduce the risk of duplicating information in this IRB Protocol form that you will need to provide in these Supplements.

Check all That Apply	Type of Research	Supplement Name
	Department of Defense The research involves Department of Defense funding, facilities, data, or personnel.	SUPPLEMENT Department of Defense
	Department of Energy The research involves Department of Energy funding, facilities, data, or personnel.	SUPPLEMENT Department of Energy

	Drug, biologic, botanical, supplement Procedures involve the use of any drug, biologic, botanical or supplement, even if the item is not the focus of the proposed research	SUPPLEMENT Drugs
	Emergency exception to informed consent Research that requires this special consent waiver for research involving more than minimal risk	SUPPLEMENT Exception from Informed Consent for Emergency Research (EFIC)
	Genomic data sharing Genomic data are being collected and will be deposited in an external database (such as the NIH dbGaP database) for sharing with other researchers, and the UW is being asked to provide the required certification or to ensure that the consent forms can be certified	SUPPLEMENT Genomic Data Sharing

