5.4 Data variables. Describe the specific data that will be obtained (including a description of the most sensitive items). Alternatively, a list of the data variables may be uploaded to **Zipline**.

See attached data collection instruments:

- Aim 1 validation questionnaire
- Aim 2 FGD guide
- Aim 3 pregnant client screening questionnaire
- Aim 3 pregnant client enrollment questionnaire

- Aim 3 pregnant client follow-up questionnaire
- Aim 3 pregnant client variables for data abstraction
- Aim 3 pregnant client verbal autopsy questionnaire
- Aim 3 nurse IDI guide

5.5 Data sources. For all types of data that will be accessed or collected for this research: Identify whether the data are being obtained from the subjects (or subjects' specimens) or whether they are being obtained from some other source (and identify the source).

If you have already provided this information in Question 5.1, you do not need to repeat the information here.

The data will be obtained from subjects' self-report and from their clinic based medical record.

5.6 Identifiability of data and specimens. Answer these questions carefully and completely. This will allow HSD to accurately determine the type of review that is required and the relevant compliance requirements. Review the following definitions before answering the questions:

Access means to view or perceive data, but not to possess or record it. See, in contrast, the definition of "obtain".

Identifiable means that the identity of an individual is or may be readily (1) ascertained by the researcher or any other member of the study team from specific data variables or from a combination of data variables, or (2) associated with the information.

Direct identifiers are direct links between a subject and data/specimens. Examples include (but are not limited to): name, date of birth, medical record number, email or IP address, pathology or surgery accession number, student number, or a collection of data that is (when taken together) identifiable.

Indirect identifiers are information that links between direct identifiers and data/specimens. Examples: a subject code or pseudonym.

Key refers to a single place where direct identifiers and indirect identifiers are linked together so that, for example, coded data can be identified as relating to a specific person. Example: a master list that contains the data code and the identifiers linked to the codes.

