See the “Research Records and Data” information in Section 8 of this document for the retention schedules for UW Medicine Records: <https://www.uwmedicine.org/recordsmanagementuwm-records-retention-schedule.pdf>

Confirm

9.5 Certificates of Confidentiality. Will a federal Certificate of Confidentiality be obtained for the research data? *NOTE: Answer “No” if the study is funded by NIH or the CDC, because all NIH-funded and CDC-funded studies automatically have a Certificate.*

No

Yes

9.6 Data and specimen security protections. Identify the data classifications and the security protections that will be provided for all sites where data will be collected, transmitted, or stored, referring to the [GUIDANCE Data and Security Protections](#) for the minimum requirements for each data classification level. ***It is not possible to answer this question without reading this document. Data security protections should not conflict with records retention requirements.***

a. Which level of protections will be applied to the data and specimens? If more than one level will be used, describe which level will apply to which data and which specimens and at which sites.

1) Level 2 data and security protections will be applied to data from nurses collected through questionnaires, interviews and focus groups.

2) Level 3 data and security protections will be utilized for text message data received by the Mobile WACH messaging platform and responded to by the nurse and data from perinatal clients' medical records, questionnaires and interviews.

- b. Use this space to provide additional information, details, or to describe protections that do not fit into one of the levels. If there are any protections within the level listed in 9.6.a which will *not* be followed, list those here, including identifying the sites where this exception will apply. For example, if you intend to store subject identifiers with study data (not permitted under requirement U9 for Risk Levels 3-5), then indicate this in the box below (e.g., "We will not adhere to requirement U9 for screening data").

NA

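### Does the short data-source answer in section 5.5 leave the Aim 3 response-time comparison with the NEO trial without data or a usable urgency label?

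*Protocol*

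**What the plan says.** The overarching aim in section 1.5 has two targets: acceptability and the effect on health workers' response time. For the second, the Aim 3 paragraph states: "We will compare nurse response time to urgent and non-urgent participant messages with the ongoing Mobile WACH NEO trial". It adds that the NEO trial runs on the unmodified platform. Section 1.8b repeats the intention: "we will compare workflow in the context of the Mobile WACH NEO RCT with workflow in an NLP-enabled variant of the same intervention".

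On labelling, the Aim 3 text says: "Participant messages will be automatically categorized by urgency". The nurse gold standard belongs to Aim 1, where nurses judge "client messages from previous Mobile WACH studies".

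On sources, the prompt of section 5.5 opens: "For all types of data that will be accessed or collected for this research". The answer is one line, naming subjects' "self-report and from their clinic based medical record". The prompt also allows the team not to repeat what section 5.1 already covers.

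Two other places bear on the point. Section 1.8a says of the platform: "The system back-end collects SMS metadata such as time stamps and delivery status". Section 9.6 sets the security level for "text message data received by the Mobile WACH messaging platform and responded to by the nurse".

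**The concern.** Set beside 1.5, section 5.5 seems to leave out the main quantitative result. A response time is the interval between a client's message and the nurse's reply. A clinic record holds neither time. Self-report could at most be stretched to the AI-NEO clients' own texts, not to a system-logged reply and not to messages from women in another trial.

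The deferral to 5.1 does not fill the gap. For Aim 3 data collection, 5.1 describes questionnaires, record abstraction, verbal autopsy and nurse interviews, but no extraction of message logs and no use of NEO messages. None of the eight instruments listed in 5.4 is, by its title, a message log.

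The label appears to depend on the same gap. The only urgency label described for Aim 3 messages is the model's, and the NEO platform has no such model. If NEO messages were split by some other rule, part of any difference between cohorts in the urgent or non-urgent group could come from the labelling and not from the interface.

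**Working it through.** The protocol states no figure on this point, so the check is a comparison of passages. For each item that the 1.5 comparison needs, the table shows whether 5.5 names it and whether the protocol supplies it elsewhere.

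| Item needed | Named in 5.5? | Elsewhere in the protocol |
|---|---|---|
| AI-NEO client messages and nurse replies | No, unless client texts count as self-report | 9.6 classes both as study data; 5.10 foresees further use of the SMS for model development |
| Message and reply times, AI-NEO | No | 1.8a: the back-end logs time stamps |
| Messages and times, NEO trial | No | 1.8a describes the same platform, lists the NEO trial in Table 1 and offers the suite's SMS data (put at 400,000 messages) to this project; Table 1 gives the NEO trial's own counts as NA |
| Link to the NEO trial | No | 1.3 nests Aim 3 within STUDY00006395; 1.5 and 1.8b state the comparison; 5.1 cites the same study number |
| Urgency label, AI-NEO | Not a source question | 1.5 and 5.1: model output |
| Urgency label, NEO trial | Not a source question | Not stated |

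**Data.** Of the two sources in 5.5, none contains reply times: 0 of 2. That describes one answer box and not the protocol as a whole. Both cohorts run on the Mobile WACH platform, whose back-end logs time stamps. Response time is therefore reply time minus message time, taken from the same kind of log in each cohort. An analyst told to carry out the comparison in 1.5 would go to those logs, and listing them in 5.5 would give the same data set.

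**Label.** There are three ways to label the messages:

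1. Run the selected model on the stored NEO messages as well. The rule is then the same in both cohorts, there is no labelling artefact, and the result describes flagged and unflagged messages.
2. Have nurses judge messages in both cohorts. The rule is again the same, and the result describes urgency as nurses see it, at the cost of extra reading.
3. Use the model in one cohort and a different rule in the other. Only this option creates an artefact.

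Nothing in the protocol points to the third. Because the NEO platform has no classifier, a label has to be added afterwards in any case, and the natural step is to use one rule for both cohorts. A comparison of response time over all messages together needs no label.

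**Size.** The documents give no urgency prevalence, sensitivity, specificity or response time. A count of flagged messages, or of the share of them truly urgent, would rest on assumed inputs. It would describe how well the classifier performs and would not measure the effect of the omission in 5.5.

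**The case for a change.** The strongest case for a change is that this is a contradiction in text the protocol itself fixes, so it cannot be put down to detail awaiting an analysis plan. Section 5.5 asks about all data, the answer leaves out the data for one of the two stated targets, and 5.1 does not make good the omission. The comparator is also wholly external: all pilot women receive the intervention, women already in another study are excluded, and section 2.8 lists no group of NEO women. A reader who wants to know what is taken from the other trial has to infer it. The remedy would be only a sentence or two.

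Much of this stands. The 5.5 answer is incomplete, it does not agree with 1.5, 1.8 or 9.6, and the protocol never spells out the extraction of NEO messages. What does not stand is the consequence. Question 5.5 asks about provenance on an ethics form and does not specify the analysis data set. The needed records are described elsewhere in the same document, and the link to the NEO trial is disclosed in 1.3, where the form asks for related applications. Whether the NEO approval covers this use is a question of permission and does not bear on the validity of the comparison.

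A sentence fixing the model's label for both cohorts would also have a cost. It would rule out nurse-judged urgency, which the protocol leaves open and which is closer to true urgency. That choice is a trade-off and not the repair of an error.

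**Conclusion.** No change to the plan follows. Section 5.5 has a clerical gap: it omits the platform's message records for AI-NEO and the NEO trial, although other sections describe or plainly imply their use. The effect on the Aim 3 result is nil, provided the analysts use the platform logs, as 1.5 and 1.8b require.

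The missing labelling rule for NEO messages is detail that an analysis plan commonly holds, and no such plan is at hand. If one rule serves both cohorts, whether model or nurse, there is no labelling artefact. If the rules differed there could be one, of unknown size and direction, but the protocol does not say they will differ.

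This conclusion rests on two assumptions: that the NEO platform stores message and reply times as 1.8a describes, and that one labelling rule is applied to both cohorts. The first is stated for the platform in general; the second is the natural reading.

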2 PARTICIPANTS

2.1 Participants. Describe the general characteristics of the subject populations or groups, including age range, gender, health status, and any other relevant characteristics.

Aim 1: model validation

- Current or previous nurse on a Mobile WACH study

Aim 2: interface design

- Current nurse on a Mobile WACH study or at ministry of health facility

Document Date & Version

08/26/2021

Version 3.6

APPLICATION IRB Protocol

Researcher Date & Version

11/12/2021

Version 1.1

Page 10 of 55

Aim 3: Pilot

- Pregnant women at 28-36 weeks gestation, age ≥ 14 , able to receive daily SMS
- Nurses working on delivering the AI-NEO pilot

2.2 Inclusion and exclusion criteria.

a. Inclusion criteria. Describe the specific criteria that will be used to decide who will be included in the research from among interested or potential subjects. Define any technical terms in lay language.

Aim 1: model validation

- Currently or previously worked as a study nurse on a Mobile WACH study

Aim 2: interface design

- Currently working as a nurse on a Mobile WACH study or at ministry of health facility

Aim 3: Pilot

- Pregnant clients
 - Pregnant
 - 28-36 weeks gestation
 - Daily access to a mobile phone (own or shared) on the Safaricom network
 - Willing to receive SMS
 - Age ≥ 14 years
 - Able to read and respond to text messages in English, Kiswahili or Luo, or have someone in the household who can help
- Nurses
 - Currently working as a nurse on AI-NEO study

b. Exclusion criteria. Describe the specific criteria that will be used to decide who will be excluded from the research from subjects who meet the inclusion criteria listed above. Define any technical terms in lay language.

Aim 1: model validation

- None

Aim 2: interface design

- None

Aim 3: Pilot

- Pregnant clients
 - Currently enrolled in another research study

2.3 Prisoners. IRB approval is required in order to include prisoners in research, even when prisoners are not an intended target population.

Is the research likely to have subjects who become prisoners while participating in the study?

For example, a longitudinal study of youth with drug problems is likely to have subjects who will be prisoners at some point during the study.

No

Yes → If yes, if a subject becomes a prisoner while participating in the study, will any study procedures and/or data collection related to the subject be continued while the subject is a prisoner?

No

Yes → If yes, describe the procedures and/or data collection that will continue with prisoner subjects

2.4 Will the proposed research recruit or obtain data from individuals that are known to be prisoners?

For records reviews: if the records do not indicate prisoner status and prisoners are not a target population, select "No". See the [GUIDANCE Prisoners](#) for the definition of "prisoner", which is not necessarily tied to the type of facility in which a person is residing.

No

Yes → If yes, answer the following questions (i – iv).

i. Describe the type of prisoners, and their location(s):

ii. One concern about prisoner research is whether the effect of participation on prisoners' general living conditions, medical care, quality of food, amenities, and/or opportunity for earnings in prison will be so great that it will make it difficult for prisoners to adequately consider the research risks. How will the chances of this be reduced?

iii. Describe what will be done to make sure that (a) recruitment and subject selection procedures will be fair to all eligible prisoners and (b) prison authorities or other prisoners will not be able to arbitrarily prevent or require particular prisoners from participating.

iv. If the research is funded by one of these federal departments and agencies (Health & Human Services; Energy; Defense; Homeland Security; CIA; Social Security Administration), and/or will involve prisoners in federal facilities or in state/local facilities outside of Washington State: check the box below to provide assurance that study team members will (a) not encourage or facilitate the use of a prisoner's participation in the research to influence parole or pardon decisions, and (b) clearly inform each prisoner in advance (for example, in a consent form) that participation in the research will have no effect on his or her parole or pardon.

Confirmed

2.5 Protected populations. IRB approval is required for the use of the subject populations listed here. Check the boxes for any of these populations that will be purposefully included. (In other words, being a part of the population is an inclusion criterion for the study.)

The WORKSHEETS describe the criteria for approval but do not need to be completed and should not be submitted.

Population	Worksheet
 Fetuses in utero	WORKSHEET Pregnant Women
 Neonates of uncertain viability	WORKSHEET Neonates
 Non-viable neonates	WORKSHEET Neonates

Pregnant women

[WORKSHEET Pregnant Women](#)

a. If you check any of the boxes above, use this space to provide any information that may be relevant for the IRB to consider.

This research proposal is focused specifically on using digital technologies (SMS) to improve neonatal mortality, practice of essential newborn care, care seeking behavior and maternal self-efficacy in Kenya. The research aims are specific to pregnant and postpartum women (including adolescent girls aged 14-17) and their babies. Kenyan regulations consider pregnant women age ≥ 14 emancipated by pregnancy and able to give consent as independent adults.

2.6 Native Americans or non-U.S. indigenous populations. Will Native American or non-U.S. indigenous populations be actively recruited through a tribe, tribe-focused organization, or similar community-based organization?

Indigenous people are defined in international or national legislation as having a set of specific rights based on their historical ties to a particular territory and their cultural or historical distinctiveness from other populations that are often politically dominant.

Examples: a reservation school or health clinic; recruiting during a tribal community gathering

No

Yes

→ If yes, name the tribe, tribal-focused organization, or similar community-based organization. The UW IRB expects that tribal/indigenous approval will be obtained before beginning the research. This may or may not involve approval from a tribal IRB. The study team and any collaborators/investigators are also responsible for identifying any tribal laws that may affect the research.

2.7 Third party subjects. Will the research collect private identifiable information about *other individuals* from the study subjects? Common examples include: collecting medical history information or contact information about family members, friends, co-workers.

"Identifiable" means any direct or indirect identifier that, alone or in combination, would allow you or another member of the research team to readily identify the person. For example, suppose that the research is about immigration history. If subjects are asked questions about their grandparents but are not asked for names or other information that would allow easy identification of the grandparents, then private identifiable information is not being collected about the grandparents and the grandparents are not subjects.

No

Yes

→ If yes, these individuals are considered human subjects in the study. Describe them and what data will be collected about them.

2.8 Number of subjects. Is it possible to predict or describe the maximum number of subjects (or subject units) needed to complete the study, for each subject group?

Subject units mean units within a group. For most research studies, a group will consist of individuals. However, the unit of interest in some research is not the individual. Examples:

- Dyads such as caregiver-and-Alzheimer’s patient, or parent and child
- Families
- Other units, such as student-parent-teacher

Subject group means categories of subjects that are meaningful for the specific study. Some research has only one subject group – for example, all UW students taking Introductory Psychology. Some common ways in which subjects are grouped include:

- By intervention – for example, an intervention group and a control group.
- By subject population or setting – for example, urban versus rural families
- By age – for example, children who are 6, 10, or 14 years old.

The IRB reviews the number of subjects in the context of risks and benefits. Unless otherwise specified, if the IRB determines that the research involves no more than minimal risk: there are no restrictions on the total number of subjects that may be enrolled. If the research involves more than minimal risk: The number of enrolled subjects must be limited to the number described in this application. If it is necessary later to increase the number of subjects, submit a Modification. Exceeding the IRB-approved number (over-enrollment) will be considered non-compliance.

No → If no, provide the rationale in the box below. Also, provide any other available information about the scope/size of the research. You do not need to complete the table.

Example: It may not be possible to predict the number of subjects who will complete an online survey advertised through Craigslist, but you can state that the survey will be posted for two weeks and the number who respond is the number who will be in the study.

Yes → If yes, for each subject group, use the table below to provide the estimate of the maximum desired number of individuals (or other subject unit, such as families) who will complete the research.

Group name/description	Maximum desired number of individuals (or other subject unit, such as families) who will complete the research Provide numbers for the site(s) reviewed by the UW IRB and for the study-wide total number; example: 20/100
Aim 1 nurses	10
Aim 2 nurses	20
Aim 3 pregnant cohort	80
Aim 3 nurses	4

